1.3 Schema

Week 1 through Week 4	Enrollment and Training

 • Total n=5 anesthesiologists, 10 CRNAs/anesthesia residents/fellows (user subjects) • Identify user subjects - anesthesiologists and their teams of CRNAs, anesthesia residents and fellows performing planned airway procedures under general anesthesia. • Obtain informed consent from willing user subjects and complete intake questionnaire • Document and record contact information for user subjects • Review user manual and device use. 	
Week 1 through Week 6	Device Use and Assessment

 • Protective device use and aerosol evacuation during airway procedures under general anesthesia on COVID-19-negative patients • Patients (patient subjects) of anesthesiologists participating as user subjects in the study will be recruited on the day of procedure. • Patient subjects will be randomized to intubation with or without the biocontainment device. • Goal of obtaining data from 150 airway procedures under general anesthesia in the device (100 with the device and 50 without the device). • Patient subject Data and data from record of airway procedure will be recorded after each device use • Quality Use Survey, including documentation of any AEs will be completed by user subjects at the end of each day • Patient experience questionnaire completed by patient subject randomized to device use within 1 week after procedure 	

- AE event summary reconciliation and review performed weekly
- Feedback on quality use data use and user suggestions given to engineering team every two weeks
- Interval assessment by the medical director of intubation data from medical record, quality use survey data, including summary of AEs, and preliminary analysis of post-training questionnaire/intake data every two weeks

Week 4 through Week 12	Device Use and Assessment, Final Data Analysis
	
• Continued use and assessment of biocontainment device if needed to meet enrollment numbers• Final Feedback on device use and user suggestions given to engineering team• Final assessment of survey data and device utilization

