2. *Situation Urgency/Emergency:* Extubation and delivery of a nebulizer treatment or suctioning are all accomplished in an orderly and timely fashion. Intubation, depending on the urgency requires a highly coordinated and efficient response and a new device may create another layer of risk by introducing another step in the intubation process. The process for device utilization will require a work flow where the provider performing/assessing the need for intubation can understand the potential risks/benefits of proceeding with intubation. **The primary goal of this study is to assess use of the device for planned airway procedures under general anesthesia to better assess the feasibility for using this device as part of aerosol generating procedures for COVID-19 patients.**

People:

1. *Human Error:* Human error is the largest risk factor for proper use of the device. Error in understanding device function, device setup, or aerosol evacuation could lead to a false sense of security in use of the device. Improper device utilization also has a risk to cause harm to the study subject. For this reason, there is a robust audiovisual and written/pictorial training program for device use with a plan for assessment of device training. An additional goal of this study will be to assess number of device uses needed to obtain proficiency.
2. *Clinical Training and Experience:* Study subjects will have a wide range of experience and training. The goal of this study is to involve stakeholders with multiple years/levels of experience in intubation procedures. We intend to track outcomes based on these variables to assess for further needs for enhanced training, healthcare burden, and overall device utilization.
3. *Patient Risk:* There is a small risk of mild patient injury with the device as well as a mild risk of claustrophobia or anxiety to the patient in the device. Patient injury from the device, small risk of abrasion or contusion if the patient sits up inside the device is unlikely to occur, and would be an adverse event if it were to occur. The preclinical feasibility indicates that the most technically challenging procedure of intubation can be performed safely with this device. All patients will be monitored while in the device and if they request to be taken out of the device or display signs of increasing anxiety/claustrophobia, the device will be removed.

Materials:

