3 STUDY OBJECTIVES AND ENDPOINTS

The objectives of this study are to evaluate efficacy of training and use by frontline healthcare workers of a biocontainment system that provides additional protection during aerosol-generating procedures with COVID-19 patients. The primary objectives of this study are: 1) Assess changes in airway procedure times with and without the biocontainment device as a function of repeated utilization and as a function of patient-associated airway factors (Mallampati score, hyomental distance, neck mobility, BMI) and user-associated airway factors (experience of user, airway device used, induction sequence) and 2) Assess adverse events, adverse device events associated with biocontainment device use. Secondary objectives include: 1) Assess the subject's comfort with using the biocontainment device, 2) Assess for additional healthcare and cognitive burden imposed by the device. 3) Survey of patient's post-procedure on experience being inside the device. Exploratory objective includes gathering specific feedback regarding possible design modifications for further iterations and design improvements with the engineering team.

OBJECTIVES	ENDPOINTS	JUSTIFICATION FOR ENDPOINTS
Primary		

 1. Assess changes in airway procedure times with and without the biocontainment device as a function of repeated utilization and as a function of patient-associated airway factors (Mallampati score, hyomental distance, neck mobility, BMI) and user-associated airway factors (experience of user, airway device used, induction sequence). 2. Assess adverse events, adverse device events associated with using the biocontainment device. 	
 1. Measuring the time for performing an airway procedure with the biocontainment device when accounting for patient and user-specific factors. Sub-analysis, based on user experience level. 2. Quantifying the number of AEs or ADEs over time to assess device safety. Breakdown of AEs/ADEs as a function of time and by user subject. 	These endpoints were chosen to assess the safety and efficacy of biocontainment device use over time. This will help assess the viability of the device as an additional layer of protection for aerosol-generating procedures.
Secondary		

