5.5 Strategies for Recruitment and Retention

User Subject Recruitment and Retention

User-subjects will be recruited from within the department of anesthesia at HUP or PPMC. They will be approached in person or via email asking for participants in a trial of a biocontainment device for planned airway procedures under general anesthesia. Information provided will include length of time for study participation, participation in device training session, participant eligibility including willingness to use the device during procedures and lift up to 10 lbs, and participant requirements in the study (completion of surveys post-utilization and training). Healthcare workers (user subjects) will be recruited based solely on these criteria

and will include attending physicians, residents, fellows, and CRNA. No specific gender, age, race or ethnicity criteria will be used in the recruitment of subjects. Fifteen (15) to twenty (20) user subjects will be recruited at the study sites over the first month of the study. We anticipate full recruitment during this time. If targets are not met during the first month, recruitment will be ongoing during the second month of the study. Healthcare workers will be recruited solely on a voluntary basis with the option to withdraw at any time from the study without any form of penalty. The consent process will explicitly state that volunteering to participate in the study, declining to participate in the study, or withdrawal from the study will not affect employment status or access to appropriate PPE as determined by hospital protocols. This study is voluntary and no compensation or additional incentives will be provided.

Patient Subject Recruitment and Retention

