9.4.2 Analysis of the Primary Efficacy Endpoint(s)

Primary Endpoints:

1. Assessment of time to complete an airway procedure with or without the biocontainment device. The time is measured as a single quantitative measure at the end of the procedure. The initial starting time (T0) is defined as “time the mask is removed from the patient just prior to initiation of the airway procedure”. End time (T1) is defined as the time that the airway procedure is completed with a secure airway defined as the

time the airway device is secured to the airway circuit. Data will be presented as median amount of time for a given procedure with or without the biocontainment device and statistical significance will be determined by analysis of variance (ANOVA). Additionally, a multiple regression model will be created using covariates of subject user experience, number of prior uses with the device, and patient specific factors (co-morbid conditions, BMI, Mallampati score). This will help determine the critical factors associated with time to use the device.

2. The total number of AEs and ADEs will be presented. This will be broken down by specific AE or ADE. Logistic regression will be used to assess possible contributing factors to AEs or ADEs including subject user experience, airway procedure performed, patient-specific factors (BMI, co-morbid conditions, Mallampati score). We anticipate a low number of AEs/ADEs and as such, statistically rigorous regression analyses may be limited by a low overall number of events.

Statistical analyses will be performed on all data points, however, a sub-analysis will be performed on participants without any missing data points.

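### The section 9.4.2 time regression has no term for repeated procedures by one user and, pooled or device-only, does not estimate the with-versus-without learning contrast in primary objective 1

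*Combined protocol and SAP*

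**What the plan says.** Section 9.4.2 analyses time to a secure airway in two ways. Medians with and without the device are compared by ANOVA. In addition, "a multiple regression model will be created using covariates of subject user experience, number of prior uses with the device, and patient specific factors". The patient factors named there are BMI, the Mallampati score and co-morbidities. The stated purpose is: "This will help determine the critical factors associated with time to use the device".

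The covariate list contains no study arm, no interaction of arm with prior uses, and nothing that identifies the user. No other part of section 9 gives a random effect, a cluster-robust variance or another repeated-measures method. Section 4.1 points to section 9.4.7 for stratification of results, but 9.4.7 only lists individual data.

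On numbers, section 1.3 gives "Total n=5 anesthesiologists, 10 CRNAs/anesthesia residents/fellows (user subjects" and 150 procedures, 100 with the device and 50 without. Section 5.5 says "Fifteen (15) to twenty (20) user subjects will be recruited". Section 6.3 randomises patients 2:1.

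Primary objective 1 in section 3 begins "Assess changes in airway procedure times with and without the biocontainment device as a function of repeated utilization". Section 2.3.3 adds "An additional goal of this study will be to assess number of device uses needed to obtain proficiency" and, on users' experience and training, "We intend to track outcomes based on these variables to assess for further needs for enhanced training".

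**The concern.** Two things go wrong if the regression is fitted as listed.

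First, a user's experience is essentially constant over a 12-week study. Its coefficient is therefore informed by 15 to 20 people, while an ordinary regression treats it as 100 or 150 independent values. The number of prior uses is a fixed learning covariate and does not absorb lasting differences in speed between users. If such differences exist beyond what experience explains, experience can be named a determinant of procedure time too easily.

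Second, the objective is a contrast: does the device-minus-control difference in time change as users gain practice? That is an arm-by-prior-uses term. The ANOVA gives only the overall arm difference, and the regression gives at most one slope.

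This regression is the only model in section 9 with experience and prior uses as predictors of time, so it is the natural source for the training and proficiency conclusions in section 2.3.3.

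**Working it through.** **The plan's own figure.** Section 9.2 gives 1.96² × 0.25 / 0.10² = 96.04, rounded up to 97. This reproduces, but it contains no clustering, arm or learning term, so it does not bear on this point.

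**Inputs.** From the documents: 15 or 20 users; 150 procedures, 100:50; significance level 0.05 (section 9.4.1; two-sided assumed). Assumed, because the documents give no value: ICC 0.05 to 0.30 for users, and normal errors.

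**1. Experience test, by formula.** For a covariate that is constant within user, with m procedures per user, the design effect is DE = 1 + (m − 1) × ICC. The large-sample type I error of the unclustered test is 2 × [1 − Φ(1.96/√DE)].

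| Base, users | m | DE, ICC 0.05 to 0.30 | Type I error |
|---|---|---|---|
| 150, 15 | 10 | 1.45 to 3.70 | 10.4% to 30.8% |
| 150, 20 | 7.5 | 1.32 to 2.95 | 8.9% to 25.4% |
| 100, 15 | 6.67 | 1.28 to 2.70 | 8.4% to 23.3% |
| 100, 20 | 5 | 1.20 to 2.20 | 7.4% to 18.6% |

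**2. The same by simulation** (10,000 trials per cell on 150 procedures, 6,000 on 100; null experience effect; ICC 0.05 to 0.30).

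| Base, users | Equal caseloads | Unequal caseloads |
|---|---|---|
| 150, 15 | 10.4% to 32.0% | 12.2% to 36.7% |
| 150, 20 | 8.7% to 26.3% | 10.5% to 31.3% |
| 100, 15 | 8.7% to 24.4% | 9.5% to 28.7% |
| 100, 20 | 7.3% to 20.1% | 8.5% to 22.8% |

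At ICC 0.01 the range over all these settings is 4.8% to 6.3%, and on 150 procedures at ICC 0 it is 4.8% to 5.3%. The arm comparison stays at 4.7% to 5.2% throughout.

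**3. Learning slope.** Suppose each prior use changes device time by −1 and control time by 0.
- Pooled fit: the slope is close to the 2:1 mix, (100 × −1 + 50 × 0)/150 = −0.67. Simulated: −0.66 without an arm term, −0.67 with an arm main effect.
- Device-only fit: −1.00. Model with the interaction: −1.00.

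Now suppose there is no device learning, but every user speeds up by 1 per case in both arms. With 10 cases per user numbered 0 to 9, case number has mean 4.5 and variance 8.25. Prior uses are then about binomial with probability 2/3. The slope of case number on prior uses is (2/3 × 8.25)/(4/9 × 8.25 + 2/9 × 4.5) = 5.5/4.67 = 1.18. A false learning slope of about 1.18 times the trend per case is therefore expected. Simulated, pooled or device-only: about −1.2 with 15 users and −1.1 with 20. The interaction gives about 0.01.

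**4. Precision of the interaction.** Its standard error is 0.071 to 0.082 (15 users) or 0.093 to 0.105 (20 users) total SD per prior use. Multiplying by 1.96 gives half-widths of 0.14 to 0.16 and 0.18 to 0.21. A user reaches on average 6.0 or 4.3 prior uses. Over the whole series the half-width is about 0.83 to 0.96 SD or 0.78 to 0.89 SD.

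**5. Check of the remedy.** With an operator random intercept and (users − 2) degrees of freedom, the experience test has type I error 2.7% to 5.6%, and the interaction test 4.0% to 6.4%. This includes unequal caseloads and an unmodelled attending variance of 0.05.

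**The case against.** The strongest reply is that the regression is a device-only model. Section 3 words the endpoint as time with the device, accounting for patient and user factors, and section 9.4.2 gives the purpose as "This will help determine the critical factors associated with time to use the device". On that reading arm cannot be a covariate, the with-versus-without comparison belongs to the ANOVA, the base is 100 procedures, and the device slope is exactly right when there is no general speed-up. The reading is plausible, and it lowers the inflation to the 100-procedure rows above. It does not remove the inflation, and it still leaves no control comparison for the slope.

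It is also fair that section 9.4.2 sets no decision threshold for these covariates and that the ICC is an assumption. The experience half therefore matters only to the extent that p-values or CIs are used to pick out factors, and only if users really differ. The false learning slope likewise depends on a general trend for which the documents give no figure; it scales with that trend.

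Finally, the interaction will be imprecise, and a linear interaction does not yield the number of uses to proficiency. Both points stand, and they determine how it should be reported.

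**Conclusion.** The point holds. Fitted as listed, the regression overstates the evidence on user experience whenever users differ beyond experience. The size depends on the unstated base and the assumed ICC, as tabulated. The learning half needs no ICC: neither a pooled nor a device-only fit estimates the contrast in primary objective 1. This should be changed, but it does not threaten the overall arm comparison.

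A reader might infer more than the documents support:
- That the arm ANOVA is invalid. It is not: patients are randomised to arm, and the test keeps its nominal level if the device effect does not vary by user.
- That training decisions rest on these p-values alone. The documents do not say so.
- That the device-only slope is always biased. It is biased only if there is a general speed-up.
- That the adverse-event logistic regression needs the same change. Section 9.4.2 already expects few events and warns that the regression may be limited, and section 3 promises "Breakdown of AEs/ADEs as a function of time and by user subject". No change to that model is part of this point.

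**What to change.** Fit one linear mixed model to all procedures, on log time if the Q-Q plots support it. Fixed effects: arm, the performing operator's number of prior device uses (counted for procedures in both arms), arm by prior uses, user experience, and the patient factors already listed in section 9.4.2. Add a random intercept for the performing operator with small-sample degrees of freedom, or use cluster-robust errors with a small-sample correction.

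Report the adjusted arm difference and the arm-by-prior-uses term as estimates with 95% CIs, not as tests. Report the device-arm slope from the same model as input to the proficiency goal in section 2.3.3. Keep the ANOVA as planned.

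The cost is SAP wording, slightly wider intervals for experience, and recording the performing operator's ID with each procedure. Sections 6.4 and 8.1 tie device records to the attending and list only the performing person's experience level, but section 10.1.3 already gives every user subject an identifier. Procedure order is needed anyway for the planned prior-uses covariate and should be captured at the same time. Videos are deleted within 14 days (section 10.1.8.1), so neither item can be recovered from them later. No change to sample size or procedures is needed.

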9 STATISTICAL CONSIDERATIONS

9.1 *Statistical Hypotheses*

We hypothesize that the biocontainment device will be a safe and effective option for performing airway procedures in patients while also providing additional protection during an aerosol generating procedure.

Primary Efficacy Endpoints:

1. We hypothesize that the time to perform an airway procedure with the biocontainment device will be equivalent to time for airway procedure without the biocontainment device. Alternatively, there will be prolonged airway procedures times with the device. This endpoint will be analyzed every two weeks.
2. We anticipate that the number of AEs or ADEs will be low and will also decrease over time. This endpoint will be analyzed on a weekly basis.

Secondary Efficacy Endpoints:

1. We hypothesize that the median Likert ratings for User subject device comfort will be weighted toward “strongly agree”. Alternatively, we will see ratings favoring “neutral” or “disagree” for user subject device comfort.
2. We hypothesize that the median Likert ratings for User subject additional healthcare burden comfort will be weighted toward “strongly disagree”. Alternatively, we will see ratings favoring “neutral” or “agree” on increased healthcare burden.
3. The median Likert ratings for the Patient Experience survey will be weighted toward minimal patient discomfort or anxiety. Alternatively, we will see ratings favoring increased patient discomfort or anxiety inside the device.
3. We anticipate that the median Likert ratings of the patient experience post-survey will indicate overall good user comfort and low levels of anxiety or claustrophobia in the device.

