9.2 Sample Size Determination

Statistical calculations:

Sample size (for unknown population size) was determined based upon a 95% confidence level (Z-score 1.96), standard deviation of 0.5, and a margin of error (confidence interval) of 10%. [[qualtrics.com/experience-management/research/determine-sample-size](https://www.qualtrics.com/experience-management/research/determine-sample-size)]

- Necessary Sample Size = $((Z\text{-score})^2 * \text{StdDev}^2 * (1-\text{StdDev}^2)) / (\text{margin of error})^2$
 - $((1.96)^2 * 0.5^2 * (1-0.5^2)) / (0.1)^2 =$
 - $(3.8416 * 0.25) / (0.01) =$
 - 96.04
 - **At least 97 performed airway procedures are needed to have adequate power to test our hypotheses for this study**

We will screen at least 175 patients, and assuming a 10-15% drop-out/screen failure rate, plan to enroll at least 150 patient subjects on a rolling basis during weeks 2 - 6 of the trial to evaluate the use of a novel biocontainment and aerosol evacuation system. The study should be adequately powered to assess secondary endpoints. Some of the sub-analyses may be underpowered depending on the characteristics of the recruited patients.

At defined intervals (see Section 1.3 Schema), we will perform interim analysis to determine changes to sample size based on subject drop out/withdrawal.

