9.4 Statistical Analyses

9.4.1 General Approach

Descriptive statistics:

- The number of subjects who utilized the protective device will be included; the level of experience and training of user subjects will be included.
- Patient subject baseline demographics, co-morbidities, smoking status, and intubation-related factors will be included.
- Objective data regarding total time for the airway procedure, number of intubation/LMA/extubation attempts, airway device used (i.e. intubation blade used and size of ETT) will be included.
- The user subjects comfort level for device use will be graded on a continuous scale, and the mean comfort level calculated as well as the range.
- The patient subjects comfort level and experience in the device will be graded on a continuous scale, and the mean comfort/experience level calculated as well as the range.
- Categories for various healthcare burdens will be provided as options for participants; the mean for most common burden will be identified; the percentage for each burden subtype will also be identified.

Inferential Tests

- A p-value of 0.05 and 95% confidence interval will be utilized when determining if the protective device results in an improvement in outcomes measures, i.e. a decrease in the number of COVID-19 cases by participants.
- Chi-square testing or ANOVA will be used.

Covariates will be collected on participants, including but not limited to subspecialty training, years of experience as a resident, fellow, or attending, as well as gender.

Assumption of normality of data points will be determined using Q-Q plots. If there are limitations to performing assumptions of normality, then appropriate non-parametric corrections would be performed.

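### The AE/ADE logistic regression is likely to be non-estimable or very unstable at the low counts expected, and no sparse-event method, interval for the AE proportion or prior-use term is specified

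*Combined protocol and SAP*

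**What the plan says.** AEs and ADEs are the second primary endpoint (sections 1.1 and 3), and section 9.4.4 refers the safety analysis back to section 9.4.2. The expectation in section 9.1 is: "We anticipate that the number of AEs or ADEs will be low and will also decrease over time".

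Item 2 of section 9.4.2 plans totals, a breakdown by type and a model: "Logistic regression will be used to assess possible contributing factors to AEs or ADEs including subject user experience, airway procedure performed, patient-specific factors". The patient factors listed are BMI, co-morbid conditions and Mallampati score. It then concedes: "We anticipate a low number of AEs/ADEs", so that "statistically rigorous regression analyses may be limited by a low overall number of events". No alternative method follows.

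Item 1 of the same section, the procedure-time model, does list number of prior device uses as a covariate. Item 2 does not.

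Time appears elsewhere. Section 3 adds a breakdown of events by time and by user, section 9.1 sets a weekly analysis, and section 9.4.5 pauses the study if events trend upward. None of these names a test, an interval or a definition of a trend.

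**The concern.** When few procedures have an event, some covariate or combination of covariates often separates procedures with an event from those without. At least one odds ratio is then infinite. Where the fit is finite, one or two events per parameter give intervals too wide to use. Because no alternative is named, the method would be chosen after the events have been seen.

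The two parts of the section 9.1 expectation also lack a matching analysis. No acceptable rate or interval is attached to a low count, so a small number in about 100 uses could be reported without saying what rate it leaves open. The listed covariates include nothing that measures decline with use. A raw breakdown by time can show a fall by chance.

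**Working it through.** **The plan's own figure.** Section 9.2 uses z = 1.96, a "standard deviation of 0.5, and a margin of error (confidence interval) of 10" percent, and concludes: "At least 97 performed airway procedures are needed to have adequate power to test our hypotheses for this study". Its second line reproduces: 1.96² × 0.25 / 0.10² = 3.8416 × 0.25 / 0.01 = 96.04, rounded up to 97. The formula as first printed would give 3.8416 × 0.25 × 0.75 / 0.01 = 72.03. In either form it is a precision calculation for one proportion near 0.5. It uses no AE rate and so does not size the AE analysis.

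**Inputs for the check.** Device procedures: 100, from section 1.3 ("100 with the device and 50 without the device"). Events: no number is given, so 2 to 30 procedures with at least one event are assumed. Coding: not given, so three codings of the five listed factors are assumed:

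- 5 parameters: one for each factor.
- 7 parameters: experience 2, procedure 2, BMI 1, any co-morbidity 1, high Mallampati 1.
- 11 parameters: experience 2, procedure 2, BMI 1, co-morbidities 3, Mallampati 3.

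Covariate frequencies are assumed, no factor has a true effect, and procedures are treated as independent.

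**Estimability.** A finite fit fails to exist when some non-trivial linear combination of the covariates completely or quasi-completely separates the outcomes. This was checked by linear programming in 400 simulated data sets per cell.

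| Events in 100 | 5 parameters | 7 parameters | 11 parameters |
|---|---|---|---|
| 2 | 84% | 100% | 100% |
| 3 | 58% | 99% | 100% |
| 5 | 23% | 84% | 100% |
| 8 | 9% | 54% | 96% |
| 10 | 3% | 39% | 93% |
| 15 | 0% | 13% | 76% |
| 20 | 0% | 7% | 67% |

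Using all 150 procedures changes no cell by more than 6 points. Events per parameter at 10 events are 10/5 = 2.0, 10/7 = 1.4 and 10/11 = 0.9.

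**Stability where a fit exists.** With the 5-parameter coding, the median 95% interval for the procedure odds ratio had an upper limit roughly 70 to 90 times its lower limit at 5 events (two runs), and about 20 times at 10 events.

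**What a low count leaves open.** The exact (Clopper-Pearson) upper limit for x events in 100 is the 0.975 quantile of Beta(x + 1, 100 − x). For x = 0 this is 1 − 0.025^(1/100) = 3.6%. For x = 1 it is 5.4%, for x = 5 it is 11.3% and for x = 10 it is 17.6%.

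**Decline over use.** With 5 events and no true trend, the chance that the second half of device uses has fewer events than the first is (1 + 5 + 10)/32 = 50%. A two-sided 0.05 trend test over 100 consecutive uses, with risk falling four-fold from first to last, has simulated power of 8%, 14%, 26%, 38% and 51% at 3, 5, 10, 15 and 20 expected events. For a two-fold fall, power is 5% to 16%.

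**The case against.** The strongest reply has four parts.

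First, a reader might infer that the model usually cannot be fitted. The documents do not support this, because they give neither an event count nor a coding. A one-parameter-per-factor model at 10 events fails in only 3% of data sets. The AE definition in section 8.3 is broad and lists anxiety, claustrophobia and intubation difficulty as expected events, so the count may not be tiny. This part stands and limits the claim, although a finite fit at such counts is still very imprecise.

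Second, the limitation is disclosed, and the regression is described as a search for contributing factors, not as the test of safety. This also stands. What remains is that no fallback is named.

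Third, a reader might infer that the safety expectation gets no estimate, or that time is ignored. Neither is so. Totals, types, a breakdown by time and user, weekly review and an upward-trend pause are all planned. They are descriptive or undefined, which is a narrower complaint. The covariate list is also worded as open, so prior use is unspecified rather than excluded. Section 9.1 words the point as an anticipation, and in a feasibility study descriptive reporting of it is defensible.

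Fourth, a prior-use term would not give a useful test at these counts, and 15 to 20 users contribute repeated procedures. Both are correct, and the fix allows for them.

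**Conclusion.** The point holds in a limited form. At the low counts the plan anticipates, the listed regression is likely to be non-estimable or very unstable, and the plan names no method for that case. At 5 events, failure ranges from about 23% to 100% across the three codings; at 10 events, from 3% to 93%. These figures rest on assumed event counts, codings and covariate frequencies, and on independent procedures.

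Separately, no interval or threshold is attached to a low AE count, and no prior-use or time term is named for the AE model. A reader might infer that zero events would be reported as proof of safety. The documents do not say so; they leave the wording of a conclusion open. This is an inexpensive improvement to the analysis and does not invalidate the safety endpoint.

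**What to change.** In section 9.4.2, item 2:

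- (a) Report the proportion of device procedures with at least one AE/ADE, and with each key type, with an exact 95% interval. Word any safety conclusion by the upper limit.
- (b) Replace the listed model with Firth-penalised logistic regression, which stays finite under separation, on a small pre-specified set of terms that includes number of prior device uses and user experience. Allow for repeated procedures by the same user where event counts permit. Show the other factors descriptively.
- (c) Report the prior-use effect as an estimate with its interval, not as a confirmatory test, and state that the breakdown by time is descriptive. Power is only about 14% to 26% at 5 to 10 events, even for a four-fold fall.

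The cost is SAP wording; no added patients or measurements are needed. There are two downsides. Fewer factors are modelled, and a per-procedure proportion requires each event to be linked to a procedure. Section 8.1 has the use survey completed after each day of use, while section 8.2 has it after each use, so the plan should say how events are assigned to procedures.
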